**VI. *CD38 antibody-opsonized cells engage in fratricide.***

We treated the AML cell lines MOLM-13, MV4-11, OCI-AML3 and THP-1 overnight with or without IFN- $\gamma$ , then incubated them for an additional 18 hours with anti-CD38 antibody and measured cell death via LDH assays. As shown in Figures 6A-D, IFN- $\gamma$  significantly enhanced the antibody-mediated killing within each respective AML cell line. To test whether this was due to a toxic effect of anti-CD38, we incubated the AML cell lines on immobilized anti-CD38 for the same length of time and found that LDH release was not affected (data not shown). This suggests that the anti-CD38 antibody led to cell-against-cell killing, which was triggered and enhanced by IFN- $\gamma$  pre-treatment.

#### 4.4 RATIONALE FOR PROPOSED STUDY

CD38 expression has been demonstrated on a small subset of leukemic stem cells which are thought to be the reservoir for leukemic relapse. Daratumumab is an FDA approved antibody targeting CD38 in multiple myeloma. AML is not an indication approved by the FDA for Daratumumab. Apart from CD38 targeting, Daratumumab also has immunomodulatory effects increasing the recruitment of T cells into the marrow. Preclinical studies from OSU have shown the efficacy of Daratumumab in AML when used in combination with IFN-gamma which has resulted in upregulation of CD38. IFN- $\gamma$  promotes graft-versus-leukemia effects without directly interacting with leukemia cells in mice after allogeneic hematopoietic cell transplantation. IFN-gamma levels are elevated in post-transplant patients post-conditioning, infections, GVHD, and during hematopoietic regeneration.

Donor lymphocyte infusion is associated with a 15-30% chance of inducing remission but can be associated with GVHD. CD38 has also been shown to be an early biomarker for development of GVHD.

We hypothesize that **(i) IFN-gamma levels will be higher in post-transplant patients than healthy donors and (ii) combination of Daratumumab and endogenous IFN-gamma will mediate antileukemic efficacy post-transplant (iii) the combination of Daratumumab and donor lymphocytes will provide potent effectors (T cells and NK cells), recruit effectors to marrow and mediate graft-versus-leukemia effect.**

Date of protocol: 10/14/2020  
Version of protocol: 7  
IND number: 139015  
Institutional protocol number: OSU 17102

IRB Approval Date: 11/24/2020

## 5 STUDY OBJECTIVES

### 5.1 PRIMARY OBJECTIVE

#### **Primary Objective for Phase I study:**

To determine the maximum tolerated dose (MTD) of Daratumumab and escalating doses of donor lymphocyte infusions (DLI) in post-HCT patients with relapsed AML and MDS transformed to AML.

#### **Primary Objective for Phase II study:**

To evaluate overall response rate to Daratumumab and DLI by week 8 in patients with post-HCT relapsed AML and MDS

### 5.2 SECONDARY OBJECTIVES

1. To assess overall response rates in MRD positive patients and in patients with overt morphological relapse
2. To assess MRD conversion rates from MRD positive to MRD negative.
3. To determine the post-relapse 6-month OS rates of patients with relapsed AML and MDS following Allo-HSCT who are treated with Daratumumab
4. To determine the rates of GVHD (both grades II-IV and III-IV) and autoimmune side effects of Daratumumab within 3 months of completion of study
5. To determine the post-relapse 6-month PFS rates of patients with relapsed AML and MDS following Allo-HSCT who are treated with Daratumumab

### 5.3 EXPLORATORY OBJECTIVES

1. To compare CD38 expression levels in myeloid blasts and IFN- $\gamma$  levels in plasma, by flow cytometry and PCR, at the time of relapse before starting Daratumumab and at progression or relapse after Daratumumab To compare peripheral blood T cell number and subsets (CD3, CD4, CD8, CD38 expression on T-reg, CD4 and CD8), T reg, B-regulatory cells, NK cell numbers and bone marrow T cell subsets, by flow cytometry, at the time of relapse before starting Daratumumab, at the time of partial/complete response to Daratumumab, and at the time of progression or relapse after Daratumumab
2. To evaluate whether Daratumumab has (i) Direct anti-leukemia effects by measuring the expression of the M1 markers CD80 and CD86 by flow cytometry and PCR (ii) Antibody-dependent cellular cytotoxicity (ADCC) and Antibody-dependent cellular phagocytosis (ADCP) by using chromium based ADCC assays, and a phagocytosis assay using antibody-opsonized sheep red blood cells as targets and (iii) Immune modulation of autologous immune system (NK cells, T cells, T-reg, B-reg, and MDSCs) in AML
3. To evaluate the effect of Daratumumab on exosome content and clearance along with other soluble factors in AML
4. To evaluate serum IFN levels pre- Daratumumab, during and post-Daratumumab
5. To evaluate whether fratricide occurs in patients treated with Daratumumab

## 6 STUDY ENPOINTS

### 6.1 PRIMARY ENDPOINT

**Phase I study:** Safety and feasibility of combination of Daratumumab and donor lymphocyte infusion.

Date of protocol: 10/14/2020

IRB Approval Date: 11/24/2020

Version of protocol: 7

IND number: 139015

Institutional protocol number: OSU 17102

**Phase II study:** Overall response rate to Daratumumab and DLI in patients with post-HCT relapsed AML and MDS

## 6.2 SECONDARY ENDPOINTS FOR PHASE II

ORR in MRD positive patients and in patients with overt morphological relapse

MRD conversion rates

- 6 month post-relapse progression-free survival
- 6 month post-relapse overall survival
- 3 month GVHD rate

## 6.3 EXPLORATORY ENPOINTS FOR PHASE I AND II

Samples will be retained and/or stored for potential future use in the OSU – Leukemia Tissue Bank for up to 10 years after completion of study. Samples will be coded to protect subject identify and only the PI ([name]) will have access to the samples. All correlative studies will be conducted only at Ohio State University.

### **Bone marrow:**

1. Expression of CD38 on bone marrow: CD38 expression and other phenotypic markers on bone marrow is checked prior to transplant. Most patients are in remission prior to transplant. Patients who were initially treated at OSU will have banked leukemia samples at the time of diagnosis. Expression of CD38 on samples at diagnosis and prior to transplant will be evaluated by flow cytometry.
2. Expression of CD38 in lymphocytes in bone marrow: Percentage of lymphocytes in bone marrow pre- and post-treatment with Daratumumab will be studied. In addition to percentage, expression of CD38 on lymphocytes will be evaluated by flow cytometry.
3. Phenotypic studies to evaluate T cell exhaustion/function will be performed on bone marrow samples pre-and post-treatment with Daratumumab at the specified time points
4. Phenotypic studies to evaluate activation status of NK-cells will be performed on bone marrow samples pre-and post-treatment with Daratumumab
5. T-cell, NK cell, B-cell, and MDSC infiltration in bone marrow will be evaluated on bone marrow samples pre-and post-treatment with Daratumumab
6. Exosomes from bone marrow will be examined at these serial times for both number and also content (protein, mRNA, and miRs)
7. Serial assessment of microenvironment with stromal cell cultures.
8. Three tubes from bone marrow will be collected at each time point.

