### **Peripheral blood:**

1. Chimerism analysis: Using single-nucleotide polymorphisms, relative contributions from donor vs. recipient in sorted CD3+ and CD33+ cells will be measured and expressed as a percentage.
2. Immune reconstitution: [name] has developed a panel called the Immunome to study reconstitution of T cells, NK cells and B cells post-transplant. Specific information regarding stages of activation of T cells is also available from this panel.
3. Immune response post Daratumumab: The Immunome panel will be performed at the following time points: Day 90, 180 and 365 (+/- 7days).

Date of protocol: 10/14/2020

IRB Approval Date: 11/24/2020

Version of protocol: 7

IND number: 139015

Institutional protocol number: OSU 17102

4. Phenotypic studies to evaluate T-cell exhaustion will be performed on bone marrow samples pre-and post-treatment with Daratumumab
5. Phenotypic studies to evaluate activation status of NK-cells will be performed on bone marrow samples pre-and post-treatment with Daratumumab
6. Measurements of cytokines including but not limited to IFN-  $\gamma$  will be measured at relapse, pre and post Daratumumab treatment.
7. Exosomes from bone marrow will be examined at these serial times for both number and also content (protein, mRNA, and miRNAs).
8. CD38, CD55, and CD59 expression in circulating blood cells will be evaluated
9. Three tubes of blood will be collected at each time point for correlative studies.

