### 11.2 SAFETY INFORMATION FOR DARATUMUMAB

Daratumumab is a CD38-directed cytolytic antibody that is FDA approved for multiple myeloma. Safety information was obtained from the package insert

(<https://www.darzalexhcp.com/shared/product/darzalex/darzalex-prescribing-information.pdf> and shown below:

1. Infusion reactions: Interrupt Daratumumab infusion for infusion reactions of any severity. Permanently discontinue the infusion in case of life-threatening infusion reactions.

Date of protocol: 10/14/2020  
Version of protocol: 7  
IND number: 139015  
Institutional protocol number: OSU 17102

IRB Approval Date: 11/24/2020

2. Interference with cross-matching and red blood cell antibody screening: Type and screen patients prior to starting treatment. Inform blood banks that a patient has received Daratumumab
3. Neutropenia: Monitor complete blood cell counts periodically during treatment. Monitor patients with neutropenia for signs of infection. Dose delay may be required to allow recovery of neutrophils.
4. Thrombocytopenia: Monitor complete blood cell counts periodically during treatment. Dose delay may be required to allow recovery of platelets.

The most frequently reported adverse reactions (incidence  $\geq 20\%$ ) in clinical trials were: infusion reactions, neutropenia, thrombocytopenia, fatigue, nausea, diarrhea, muscle spasms, back pain, pyrexia, cough, dyspnea, peripheral edema, peripheral sensory neuropathy and upper respiratory tract infection

Patients with AML or MDS transformed to AML have pre-existing thrombocytopenia and neutropenia; abnormalities in blood counts will be attributed to underlying disease.

The effects of Daratumumab on the developing fetus/embryo is not known. Patients will be counselled to use effective contraception methods after transplant and specifically during the time period of study participation and study follow-up.

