Demographical and clinical characteristics of study patients will be described using mean and standard deviation, median and range, or frequency and percent depending on the data type and distribution. Overall survival (OS) will be defined as the time from the first treatment of Daratumumab to death or last contact date if no death. Progression free survival (PFS) will be defined as the time from the first treatment of Daratumumab to the date of progression or death or last clinical assessment date if no progression or death. Kaplan-Meier curves will be generated to estimate OS/PFS at 6 months. The association between patient characteristics and OS/PFS will be evaluated in univariable Cox proportional hazard regression model.

To examine the rate of GVHD (both grade II-IV and III-IV), the event will be onset of GVHD and time to GVHD will be defined as the period of time from first treatment of Daratumumab to the onset of GVHD. Death and early relapse without GVHD will be competing risks. Cumulative incidence rate of GVHD at 3-month with 95% confidence intervals will be estimated from the cumulative incidence curves. Competing risk regression analysis will be conducted to estimate the association between patient characteristics and GVHD.

For pre/post-treatment comparisons in the correlative part of the study, a paired t-test will be applied. Two-tailed p values <0.05 will be considered statistically significant in all analyses.

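### Lymphocyte and T-cell CD38 is compared before and after daratumumab by flow cytometry alone, with no stated way to tell a real fall in CD38 from drug blocking the detection antibody

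*Combined protocol and SAP*

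**What the plan says.** Three CD38 comparisons in the protocol have a stated method.

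- **Marrow lymphocytes (6.3, Bone marrow, item 2).** The item is framed around treatment: "Percentage of lymphocytes in bone marrow pre- and post-treatment with Daratumumab will be studied". It continues: "In addition to percentage, expression of CD38 on lymphocytes will be evaluated by flow cytometry". No other method is listed.
- **T-cell subsets (5.3, objective 1).** The aim is "To compare peripheral blood T cell number and subsets (CD3, CD4, CD8, CD38 expression on T-reg, CD4 and CD8", by flow cytometry, before daratumumab, at response, and at progression or relapse. PCR is not listed here.
- **Myeloid blasts (5.3, objective 1).** CD38 is compared "by flow cytometry and PCR, at the time of relapse before starting Daratumumab and at progression or relapse after Daratumumab".

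The synopsis places a marrow between doses 3 and 4 and another after week 8. The study calendar (12.1.3) puts the last weekly visit at Day 50 and the final marrow at Day 57-71. It schedules research blood at every weekly visit through Day 50.

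Section 16.2 gives the test: "For pre/post-treatment comparisons in the correlative part of the study, a paired t-test will be applied". Significance is two-tailed at 0.05.

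The text names no CD38 detection clone or epitope, no measurement of bound daratumumab, no control spiked with drug and no washout.

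**The concern.** Flow cytometry reads CD38 by binding a labelled antibody to it, and the treatment is itself an antibody to CD38. Baseline samples are free of drug and later ones are not. If the two antibodies compete for the same site, any bias runs one way, downward, and only in the later member of each pair. Pairing cannot cancel it, and more patients only make a false result more certain.

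The direction matters because it matches what the investigators would expect to see. Section 4.3 reports that a CD38-expressing regulatory T-cell subset falls after daratumumab. A masked reading would look like confirmation. Three explanations for a lower signal are then confounded: less CD38 per cell, loss of CD38-positive cells, and CD38 that is present but covered by drug. The first two are biological findings; the third is a measurement artefact.

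**Working it through.** **Does the chain hold in the text?**

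1. The drug binds the measured antigen (4.4 describes daratumumab as targeting CD38).
2. Lymphocyte and T-cell CD38 rests on flow alone (5.3, 6.3).
3. Scheduled later samples fall under or soon after exposure. The eighth weekly dose is on Day 1 + 7 × 7 = Day 50. The final marrow is therefore 57 − 50 = 7 to 71 − 50 = 21 days after it. The earlier marrow falls between doses 3 and 4.
4. The comparison is tested by a paired t-test, two-sided 0.05 (16.2).
5. No step separates masking from a real change.

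**How large could the effect be?** The plan gives no sample size, SD or power for these comparisons, so there is no figure to reproduce. The calculation below is an illustration.

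Assumptions not in the documents:
- true CD38 is unchanged;
- a fraction m of CD38 is unreadable after dosing;
- readings are compared as natural logs;
- the within-patient log difference has SD 0.6 or 0.8;
- there are 10 or 20 complete pairs (the plan's phase II size is 25 patients).

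The shift in the mean log difference is δ = ln(1 − m). The noncentrality is λ = δ√n / SD. The rejection probability is P(T < −c) + P(T > c), where T is noncentral t with n − 1 degrees of freedom and noncentrality λ. The critical value c is 2.093 for n = 20 and 2.262 for n = 10.

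Worked example, n = 20, SD 0.6, m = 0.20: δ = ln 0.8 = −0.223; λ = −0.223 × 4.472 / 0.6 = −1.66; rejection probability 0.35.

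| Masked fraction m | δ | n = 20, SD 0.6 | n = 20, SD 0.8 | n = 10, SD 0.6 |
|---|---|---|---|---|
| 0% | 0 | 5% | 5% | 5% |
| 10% | −0.105 | 12% | 9% | 8% |
| 20% | −0.223 | 35% | 22% | 18% |
| 30% | −0.357 | 71% | 47% | 39% |
| 50% | −0.693 | 99.8% | 96% | 90% |

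At m = 0 the 5% splits evenly, so a false decrease occurs in 2.5%. From m = 20% upward almost all rejections are false decreases.

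**The case against.** The strongest reply is that the error needs a competing reagent, and the documents do not say that one will be used. Section 6.3 lists assays at headline level and gives no clone or panel for any marker. All correlative work is done at one institution, whose group describes its own CD38 flow work in 4.3, and the laboratory may already use a non-competing antibody. This stands as a limit on the claim: the text supports only that no safeguard is stated. It does not remove the point, because what the comparison can conclude depends on that choice.

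A reader might infer four stronger things that the documents do not support.

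- **That blast antigen loss would be falsely reported as an escape mechanism.** Blast CD38 is also measured by PCR, and transcript level is not affected by drug sitting on the surface protein. This is a partial cross-check, although the plan does not describe it as a masking control.
- **That CD38-gated subsets would be misclassified.** No subset is said to be gated on CD38. On T cells it is listed as a readout.
- **That samples during maintenance are affected.** The maintenance calendar lists no research samples, and marrow in that period is at the physician's discretion.
- **That the plan recognises the problem.** Section 11.2 lists "Interference with cross-matching and red blood cell antibody screening", which concerns blood-bank testing, not a flow antibody failing to bind CD38.

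The blood-cell item in 6.3, "CD38, CD55, and CD59 expression in circulating blood cells will be evaluated", adds little, since it states no method, time point or comparison.

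The illustration also assumes the bias that it then shows. It indicates how sensitive the test would be to masking; it is not evidence that masking occurs.

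**Conclusion.** The concern holds for CD38 on marrow lymphocytes and on regulatory, CD4 and CD8 T cells. As written, a significant post-dose fall in these readouts could not be attributed to lower expression or to depletion of CD38-positive cells, because blocking by bound daratumumab is not excluded.

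The size is conditional on the reagent. With a reagent that does not compete, the test keeps its nominal 5%. With 20 pairs and SD 0.6, 10% to 30% masking raises this to between 12% and 71%. The masked fraction, the SD, the log scale and the number of pairs are all assumptions. The timing argument covers the scheduled samples; a sample taken at a late progression, well after the last dose, might carry less bound drug.

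The endpoints are exploratory. The MTD, the overall response rate and the secondary endpoints are not affected.

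**What to change.** In 5.3 and 6.3:

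1. State that post-dose lymphocyte and T-cell CD38 will be read with a detection reagent that daratumumab does not block. Verify this by reading an aliquot of each baseline sample with and without added daratumumab.
2. If no such reagent is used, label post-dose values as unbound CD38 only, and draw no conclusion about CD38 loss from them.
3. For blasts, base any statement of CD38 loss on agreement between flow and the PCR already planned.

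This removes masking as an explanation. It does not by itself separate lower expression per cell from depletion of CD38-positive cells, but both are real effects of interest.

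The cost is a reagent choice and one added tube from the baseline research sample already collected, with no extra patient procedure. If the laboratory already uses a non-competing reagent, stating it and adding the baseline check is enough. The choice should be made before samples are analysed, because readings on fresh cells may not be repeatable.

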## 10 MANAGEMENT OF CLINICAL EVENTS

### 10.1 CYTOPENIAS

Bone marrow biopsies will be done at time of consent, prior to DLI and at week 8. Additional Bone marrow biopsies can be done at any time at discretion of treating physician. If bone marrow shows persistent disease, cytopenias would be attributed to persistent leukemia.

Transfusions will follow institutional guidelines which typically are to keep Hgb > 7gm/dL and platelet (PLT) count more than 10K/ $\mu$ l.

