#### 12.1.3 STUDY RELATED PROCEDURES AND STUDY CALENDAR

	Screening a	Pre-1 st Dose Daratumumab	Post-1 st Dose Daratumumab	Week 2	Week 3	Week 4	Week 5	Week 6	Week 7	Week 8	Long Term Follow-up
		Day 1	Day 3 or 4	Day 8	Day 15	Day 22	Day 29	Day 36	Day 43	Day 50	Day 57-71
Informed Consent	X										
Medical history	X										
Physical Exam & Vital Signs	X	X	X	X	X	X	X	X	X	X	
Pregnancy Test (if applicable)	X										
Medication Record	X		X	X	X	X	X	X	X	X	
Performance Status	X		X	X	X	X	X	X	X	X	
Blood Draw (Complete Blood Count)	X	X	X	X	X	X	X	X	X	X	
Blood Draw (Complete Metabolic Panel)	X		X	X	X	X	X	X	X	X	
GVHD Assessment	X	X	X	X	X	X	X	X	X	X	
Donor Lymphocyte Infusion (DLI)						X					
Adverse Event Monitoring	X	X	X	X	X	X	X	X	X	X	
Bone Marrow Biopsy	X					(Pre-DLI) X					X
Research Bone Marrow samples (3 green tops of 6 ml each)	X					X					X
Research blood samples (2 green tops(6 ml each) and one red top (6 ml))	X	X	X	x	X	X	x	X	X	x	

a Screening window is 28 days.

The bone marrow biopsy at week 4 can be done at week 3, but it has to be done before the DLI. So, if the DLI can be arranged at week 4, then the marrow will be done week 3. For patients deemed eligible to receive maintenance therapy, the following procedures will be performed.

Daratumumab will be administered if PLT count is > 100K and ANC> 500.

Date of protocol: 10/14/2020

IRB Approval Date: 11/24/2020

Version of protocol: 7

IND number: 139015

Institutional protocol number: OSU 17102

Week b	Start of Daratumumab Maintenance a													
	Week 9	Week 11	Week 13	Week 15	Week 17	Week 19	Week 21	Week 23	Week 25	Week 29	Week 33	Week 37	Week 41	Week 45
CBC	x	x	x	x	x	x	x	x	x	x	x	x	x	x
Vital signs	x	x	x	x	x	x	x	x	x	x	x	x	x	x
GVHD assessment	x	x	x	x	x	x	x	x	x	x	x	x	x	x
Performance status	x	x	x	x	x	x	x	x	x	x	x	x	x	x
Adverse event monitoring	x	x	x	x	x	x	x	x	x	x	x	x	x	x

a) Daratumumab maintenance, a schedule of 16mg/kg every 2 weeks for 16 (8 doses) weeks and then monthly for 6 months will be given.

b) Daratumumab can be given +/- 3 days but there has to be a week interval between doses.

marrow during Daratumumab maintenance is at the discretion of the physician and will be considered standard of care.

Date of protocol: 10/14/2020  
Version of protocol: 7  
IND number: 139015  
Institutional protocol number: OSU 17102

IRB Approval Date: 11/24/2020

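### Immune changes are credited to daratumumab, but the paired test names no sample pair, and the 'post' sample may follow the donor lymphocyte infusion

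*Combined protocol and SAP*

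**What the plan says.** **Effect credited.** Exploratory objective 2 in Section 5.3 asks whether daratumumab produces "Immune modulation of autologous immune system (NK cells, T cells, T-reg, B-reg, and MDSCs) in AML". The marrow endpoints in Section 6.3 follow the same wording: "T-cell, NK cell, B-cell, and MDSC infiltration in bone marrow will be evaluated on bone marrow samples pre-and post-treatment with Daratumumab". Neither mentions the DLI.

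**Times named.** Exploratory objective 1 in Section 5.3 compares T-cell subsets and other immune cells before daratumumab with samples taken "at the time of partial/complete response to Daratumumab, and at the time of progression or relapse after Daratumumab". These times are not tied to the DLI date. The Immunome panel for immune response after daratumumab (Section 6.3, Peripheral blood) is set for Days 90, 180 and 365, with no stated day origin.

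**Test.** Section 16.2: "For pre/post-treatment comparisons in the correlative part of the study, a paired t-test will be applied". Also: "Two-tailed p values <0.05 will be considered statistically significant in all analyses". No pair of visits is named and nothing separates the DLI from daratumumab.

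**Sampling.** Section 10.1: "Bone marrow biopsies will be done at time of consent, prior to DLI and at week 8". The calendar in Section 12.1.3 marks research marrow at screening, in the week 4 column and at Day 57-71, with research blood from screening through week 8. Of the middle marrow it says: "The bone marrow biopsy at week 4 can be done at week 3, but it has to be done before the DLI". The synopsis (study logistics) places that marrow between doses 3 and 4.

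**The concern.** The objective is about daratumumab, but from dose level 2 onwards patients receive donor T cells part-way through treatment. The documents give reason to expect both agents to move the same cells. Section 4.3 reports more CD8+ T cells in blood and marrow after daratumumab. Section 4.2 reports, in chronic myeloid leukaemia, a larger rise in marrow T cells after DLI among responders than non-responders.

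A paired comparison from baseline to any post-DLI sample tests for no change under both agents together. If its result is reported under the present endpoint wording, a change caused by the DLI is labelled as daratumumab immune modulation. Because the pair is open, it could also be chosen after the data are seen. The hypotheses in Section 4.4 distinguish daratumumab acting with endogenous interferon-gamma from daratumumab plus donor lymphocytes. An analysis that blurs the two cannot inform that distinction.

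**Working it through.** **1. The plan's own figure.** Section 16 gives 25 Phase II patients, rejecting at 6 or more responders (10% versus 30%, alpha 0.05, power 0.80). Exact binomial:

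- P(X ≥ 6 | n = 25, p = 0.10) = 0.0334
- P(X ≥ 6 | n = 25, p = 0.30) = 0.8065

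The figure reproduces and does not depend on the correlative tests. For those tests the plan states no sample size, SD, effect size or power.

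**2. Where each sample sits** (dose levels 2 and 3 and Phase II, patients who receive the DLI):

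| Sample | Planned daratumumab before it | After DLI? |
|---|---|---|
| Screening marrow | none | no |
| Day 1 pre-dose blood | none | no |
| Pre-DLI marrow (week 3 or 4) | about 3 doses | no |
| Weekly blood up to the DLI | depends on DLI date | no |
| Week 8 blood; Day 57-71 marrow | through week 8 | yes |
| Immunome panel, Days 90, 180, 365 | full course | yes, if days run from first dose |

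A DLI-free contrast is therefore collected but not designated as the analysis.

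**3. What each contrast estimates.** Let D1 be the mean change from baseline to the pre-DLI sample. Let D2 be the further change to week 8 from continued daratumumab, and δ the change due to DLI.

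- Baseline to pre-DLI: D1
- Baseline to week 8: D1 + D2 + δ

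The second contrast identifies only the sum. With D1 = D2 = 0, its mean is δ.

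**4. Chance of rejection when only the DLI acts.** Write d = δ / SD of the paired difference, for n pairs. The paired t statistic is noncentral t with n − 1 degrees of freedom and noncentrality d√n, so

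P(reject) = P(T > c) + P(T < −c), where c is the 97.5% point of t with n − 1 degrees of freedom.

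Example: n = 25, d = 0.5 gives noncentrality 0.5 × 5 = 2.5, c = 2.064 and P = 0.670.

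| Pairs | d = 0.2 | d = 0.3 | d = 0.5 | d = 0.8 |
|---|---|---|---|---|
| 25 | 16% | 30% | 67% | 97% |
| 15 | 11% | 19% | 44% | 82% |
| 10 | 9% | 14% | 29% | 62% |

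A simulation of 100,000 trials with 25 pairs agrees: baseline to week 8 rejected in 30.1%, 67.0% and 97.0% of runs at d = 0.3, 0.5 and 0.8, while baseline to pre-DLI rejected in 5.0% each time. That 5.0% assumes nothing other than the DLI shifts the cells.

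The values of d are assumptions, because the documents give no size for a DLI effect on these cells. So are the numbers of pairs: 25 is the Phase II sample size, and the smaller values allow for patients who leave before a late sample.

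**The case against.** A reader might infer that the plan pairs screening with week 8, so that the test will reject whenever the DLI alone changes the cells. The documents do not support that. Nothing defines 'post' as week 8, several Section 6.3 items refer to serial time points, and an analyst could use the pre-DLI marrow without departing from the text. Nor do all response samples follow the DLI. Section 12.2 lists the pre-DLI marrow as a disease assessment, and the synopsis (special situations) provides for patients who respond before the DLI. Rejection is also a probability that depends on assumed shifts; showing that a t-test detects an added shift says nothing about how large the shift is here.

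A reader might also extend the point to the CD80/CD86 markers in objective 2. The documents show no route by which infused CD3 cells would distort those.

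Three further objections have weight. A baseline-to-week-8 contrast is legitimate for the combination hypothesis, so the fault lies in the label. The pre-DLI contrast is also uncontrolled: under the synopsis logistics the screening marrow can precede withdrawal of immunosuppression, and Section 8.1 allows cytoreduction before daratumumab. Finally, no primary or secondary endpoint, dose decision or sample size uses these tests.

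All of this limits the size of the point. It does not answer the gap: the pair is unnamed, the named times usually follow the DLI, and the wording credits daratumumab either way.

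**Conclusion.** The concern stands as an unspecified contrast joined to a daratumumab-only label. The data needed to separate the DLI are already scheduled. If a post-DLI sample is used as 'post', a significant result cannot be assigned to daratumumab. With no daratumumab effect at all, the chance of such a result is 9% to 97% over the assumed ranges (0.2 to 0.8 SD of the paired difference, 10 to 25 pairs), against a nominal 5%. That range is illustrative; the confounding itself does not depend on it.

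A reader might also take the pre-DLI contrast as proof of a causal daratumumab effect. It removes the DLI, but remains a pre/post change without a control.

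The consequence is confined to exploratory reporting. This is a cheap improvement.

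**What to change.** In Section 16.2, for patients who receive the DLI:

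1. Name baseline (screening marrow; pre-dose-1 blood) to the last pre-DLI sample as the DLI-free contrast, reported as change during daratumumab before DLI.
2. Report pre-DLI to the Day 57-71 marrow or week 8 blood, and baseline to week 8, as change under daratumumab plus DLI, not as daratumumab effects.
3. Classify each response and progression sample as pre- or post-DLI from the actual infusion date.
4. Show dose level 1 separately as supportive daratumumab-only data. Note that it is small (at most six evaluable patients per donor cohort under Section 16) and may include never-transplanted patients (Section 8.1).

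The cost is a few sentences and a different pairing of scheduled samples, with no new procedure. The downsides should be stated in the plan. Contrast 1 reflects about three doses rather than eight, so it misses a late daratumumab effect. It may also reflect immunosuppression withdrawal or cytoreduction, so it should not be described as a proven causal effect.
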